and age. Model over-fitting will be avoided by considering the number of parameters in the model and the number of responders in the sample. Continuous endpoints will be analyzed using either two-sample t-test or ANOVA, or non-parametric methods Wilcoxon Rank Sum test or Kruskal-Wallis test. Multivariable regressions (general linear models) will be conducted to examine the treatment effect while adjusting for important covariates such baseline 6MWD, functional status, and age. We have designed the study to minimize the potential for missing data. Subjects who drop out will be replaced up to a total of 35 per group. Nevertheless, in the event we have missing data, a multiple-imputation procedure as implemented in the *aregImpute* function in the Hmisc package in R (R Package; Version 3.0-10) will be used to assess the impact of missing data. The analyses with imputation will mainly serve as sensitivity analyses.

Brief Table of Contents

1.0	Background & Significance.....	18
2.0	Objectives and Specific Aims	20
3.0	Screening, Subject Selection, and Randomization.....	23
4.0	Study Designs	24
5.0	Data Collection	27
6.0	Assessments of Efficacy and Outcome Measures	31
7.0	Statistical Considerations	39
8.0	Study Risks and Discomforts.....	42
9.0	Quality Control.....	44
10.0	Data and Safety Monitoring and Reporting	45
11.0	Safety and Adverse Events	47
12.0	Confidentiality of Study Data	53
13.0	Ethical Considerations.....	55

Contents

Protocol Summary	1
Abstract.....	17
1.0 Background & Significance.....	18
1.1 Morbidity, mortality, and limitations of medical therapy in pulmonary arterial hypertension.	18
1.2 Insulin resistance in PAH.	18
1.3 Functional impairment and efficacy of exercise.....	18
1.4 Mechanisms of the beneficial effects of physical activity in PAH.....	19
1.5 Mobile health tools to promote behavioral change.....	19
1.6 Metformin in PAH.....	20
2.0 Objectives and Specific Aims	20
2.1 Objectives	20
Primary Aim:.....	20
Secondary Aims:	20
3.0 Screening, Subject Selection, and Randomization	23
3.1 Recruitment of Study Sample.....	23
3.2 Inclusion/Exclusion Criteria	23
3.3 Study Arm Assignment, Randomization, and Subject Retention.....	24
4.0 Study Designs	24
4.1 Overview	24
4.2 Monitoring Device	25
4.3 Fitbit Application and Data Management	25
4.4 mHealth Intervention	25
4.5 Run-in Period and Step Count Targets	26
4.6 Metformin or Placebo	26
4.7 Remuneration.....	26
5.0 Data Collection	27
5.1 Consent.....	27
5.2 Study Visits and Contacts	27

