1.8 Recruitment of Study Sample

Patients will be recruited from the Center for Pulmonary Vascular Disease (CPVD) at Vanderbilt University Medical Center (Nashville, TN), the Pulmonary Hypertension Clinic at Mayo Clinic (Rochester, MN), and the Pulmonary Hypertension Program at Cleveland Clinic (Cleveland, OH). Study sites may be contacting, communicating, and recruiting participants by, 1) telephone, 2) email using their assigned institution email address or, 3) through a secure patient portal and associated electronic medical record.

Potentially eligible subjects will be pre-screened and informed about that study to determine if they have an interest in enrolling. After the initial pre-screening, the subject will provide in-person informed consent or e-consent before any study procedures are performed.

1.9 ResearchMatch.org will also be utilized as a recruitment tool for this protocol. ResearchMatch.org is a national electronic, web-based recruitment tool that was created through the Clinical & Translational Science Awards Consortium in 2009 and is maintained at Vanderbilt University as an IRB-approved data repository (see IRB #090207).Inclusion/Exclusion Criteria

Inclusion criteria:

- Adults aged 18 or older.
- Diagnosed with idiopathic, heritable, connective tissue disease – associated PAH, or drug- or toxin-associated pulmonary arterial hypertension (PAH) according to World Health Organization consensus recommendations.
- Repaired simple congenital heart disease or unrepaired ASD
- Stable PAH-specific medication regimen for three months prior to enrollment. Subjects with only a single diuretic adjustment in the prior three months will be included. Adjustments in IV prostacyclin for side effect management are allowed.
- Subjects must own a Bluetooth capable modern smartphone capable of receiving and sending text messages and an active data plan.
- FEV1 > or = 60% predicted and no more than mild abnormalities on lung imaging
- WHO Functional Class I-III
- Ambulatory

Exclusion criteria:

- Prohibited from normal activity due to wheelchair bound status, bed bound status, reliance on a cane/walker, activity-limiting angina, activity-limiting osteoarthritis, or other condition that limits activity.
- Pregnancy
- Diagnosis of PAH etiology other than idiopathic, heritable, connective tissue disease – associated PAH, or associated with drugs or toxins
- Drug and toxin associated PAH patients with active drug use
- WHO Functional class IV heart failure

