1.10 Study Arm Assignment, Randomization, and Subject Retention

Participants will be assigned to either intervention, both interventions, or no intervention arms after the run-in period in a random manner until 40 participants are enrolled into each arm. Permuted block randomization stratified by WHO functional class (I/II vs. III) will be used to ensure approximate balance of treatment groups within each stratum over time. Based on our previous studies in PAH subjects in our catchment area, African Americans will represent approximately 16% of the study population. Randomization will be performed in small blocks, which vary in size. Investigators will be unaware of the size or order of the blocks. Projected dropout during the 12 week study has been incorporated into the power calculations. The Data Safety Monitor Board may be unblinded at any time to investigate possible adverse events. Procedures for reporting adverse events are outlined in section 7.0.

The group randomization code will be maintained by the research coordinator. The code is to be broken only if knowledge of group assignment for that subject is required to initiate appropriate therapy of an adverse event (AE) or if the safety of the subject is at serious risk without knowledge of the group assignment. The decision to unmask will be made by the PI and/or Co-PI. The Data Safety Monitoring Board will be notified as soon as possible.

Study Designs

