- To compare and define the screening plasma metabolomics profiles, including all amino acids and lipidomics, of responders and non-responders to mHealth intervention or no intervention and/or metformin at week 12.
- To assess the capacity of metabolomics profiles and clinical features at screening to predict response to the mHealth intervention or no intervention and/or metformin or placebo groups at week 12.
- To assess the capacity of change in metabolomics profile and clinical features from screening to predict response to the mHealth intervention or no intervention and/or metformin or placebo groups at week 12.
- To assess the effect of a mHealth intervention or no intervention and/or metformin or placebo on safety and tolerability in PAH subject over 12 weeks.
- To assess the fidelity of data collection and text transmission of a mHealth intervention over 12 weeks
- To assess the effect of a mHealth intervention or no intervention and/or metformin or placebo on patient satisfaction at week 12
- To assess the effect of a mHealth intervention or no intervention and/or metformin or placebo on dropout rates over 12 weeks.
- To assess the effect of a mHealth intervention or no intervention and/or metformin or placebo on PAH-related hospitalizations over 12 weeks.
- To assess the effect of a mHealth intervention or no intervention and/or metformin or placebo on medication regimen escalation/reduction over 12 weeks.
- To assess the effect of a mHealth intervention or no intervention and/or metformin or placebo on incidence of death over 12 weeks.

1.21.1 *Response to Therapy*

Response to therapy bot in will be classified as a binary yes or no response to therapy. A responder is defined by 10% or greater improvement in 6MWD over screening or improvement of at least one FC at week 12.

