1.22.5 WHO Functional Class

The WHO functional classification for PAH has been modified from the well-known New York Heart Association functional classification. This functional classification is based on symptoms, with Class I being defined by no symptoms, Class II as having mild limitation in physical activity, Class III as having markedly limited physical activity and Class IV as being unable to perform any physical activity. The WHO functional class will be assessed at screening and week 12 visits.

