1.24 Statistical Analysis

The primary analyses will focus on metformin vs placebo, exercise vs placebo, and metformin + exercise vs placebo comparisons on the primary endpoint. Since the evaluation of metformin or exercise will be reported as if they were independent studies and the combination arm versus placebo comparison serves to corroborate findings of the two separate comparisons, in addition to evaluating an additive or synergistic effect, we will not adjust for multiple comparisons. For binary endpoints, the Pearson chi-square or Fischer's exact test will be used to assess between treatment arms difference. Logistic regressions will be conducted to examine the treatment effect while adjusting for important covariates such as baseline 6MWD, functional status, age, and study site. Model over-fitting will be avoided by considering the number of parameters in the model and the number of responders in the sample. Continuous endpoints will be analyzed using either two-sample t-test or ANOVA, or non-parametric methods Wilcoxon Rank Sum test or Kruskal-Wallis test. Multivariable regressions (general linear models) will be conducted to examine the treatment effect while adjusting for important covariates such as baseline 6MWD, functional status, age, and study site. We have designed the study to minimize the potential for missing data. Subjects who drop out will be replaced up to a total of 35 per group. Nevertheless, in the event we have missing data, a multiple-imputation procedure as implemented in the aregImpute function in the Hmisc package in R (R Package; Version 3.0-10) will be used to assess the impact of missing data. The analyses with imputation will mainly serve as sensitivity analyses.

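### The primary composite is compared with an unstratified Pearson or Fisher test despite randomisation stratified by WHO class, the adjusted model is left unranked and open, and own baselines are unnamed for continuous endpoints other than 6MWD

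*Combined protocol and SAP*

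**What the plan says.** - **Randomisation (1.10):** "Permuted block randomization stratified by WHO functional class (I/II vs. III) will be used".
- **Primary endpoint (1.21.1):** "A responder is defined by 10% or greater improvement in 6MWD over screening or improvement of at least one FC at week 12".
- **Binary endpoints (1.24, repeated in the Protocol Summary under Data Analysis):** "For binary endpoints, the Pearson chi-square or Fischer's exact test will be used to assess between treatment arms difference". No rule chooses between the two tests.
- **Adjusted models (1.24):** logistic and general linear models follow, "adjusting for important covariates such as baseline 6MWD, functional status, age, and study site". The summary's list is shorter: "adjusting for important covariates such baseline 6MWD, functional status, and age". Neither place says whether the test or the model is primary.
- **Continuous endpoints (1.24):** "Continuous endpoints will be analyzed using either two-sample t-test or ANOVA, or non-parametric methods", followed by the linear models with the same covariates. Most are defined in the summary as between-group differences at week 12; muscle fatigue is a change.
- **Baselines:** section 1.23 puts step counts, activity, emPHasis-10, echo, MRS, muscle testing and blood sampling at screening and week 12. Section 1.15 defines a run-in baseline for steps.

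**The concern.** Two baseline variables are tied to the composite by its definition. Eligibility is "WHO Functional Class I-III", and section 1.22.5 describes the classes "with Class I being defined by no symptoms", so a class I patient cannot improve a class and can respond only by walking further. The 10% walking threshold also rises with baseline distance. A test that ignores a prognostic stratum used in randomisation becomes conservative, and one that ignores a prognostic covariate loses power.

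The plan lists both variables for its logistic model but does not say that this model decides the primary question. It does not fix the list or state that functional status means the I/II v III factor. The result could therefore rest on Pearson, Fisher or a model with a covariate set chosen later.

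For continuous endpoints, 6MWD is the only one whose own baseline is among the listed covariates. Without it, stable between-patient differences in weight, emPHasis-10, HOMA-IR, NT-proBNP, echo or muscle measures stay in the error term.

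**Working it through.** **1. The plan's own figure.** Section 1.26 gives 0.40 + 0.50 − 0.17 = 0.73 for active treatment, 0.40 for placebo, 80% power and 0.05 type I error. Sidedness is not stated; two-sided is assumed. The pooled-variance two-proportion formula without continuity correction gives 35 per group, as stated (approximate power 80.9%). With continuity correction it gives 41. The stated size therefore matches an unadjusted Pearson comparison.

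**2. Exact binomial enumeration, 35 per arm.**

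| Rates | Pearson | Fisher |
|---|---|---|
| 73% v 40% | 79.8% | 72.7% |
| 65% v 40% (assumed) | 53.5% | 44.1% |
| 40% v 40% (size) | 4.8% | 2.8% |

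At the planned rates the choice between the two named tests is worth 79.8 − 72.7 = 7.1 points.

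**3. How prognostic is the stratum?** The documents give no stratum rates. With the 1.26 figures, a treated class I patient responds at 40% (walking only) and other treated patients at 73%. If class I is 10, 25 or 50% of the I/II stratum (assumed), that stratum's treated rate is 69.7, 64.8 or 56.5%. Against 73% the log odds ratios are 0.16, 0.39 and 0.73. In the control arm, if walkers are the same share of responders (0.40/0.73), they are 0.08, 0.19 and 0.40. The two-arm averages are 0.12, 0.29 and 0.57.

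**4. How prognostic is baseline 6MWD?** Take P(change ≥ 0.1 × baseline), with normal change, SD 54 or 61 m (section 1.3), and assumed mean change −15 to +30 m and baselines 250 to 450 m. The slope is 0.26 to 0.33 per 100 m for the walking component alone. The composite is walking or class, so the slope shrinks. Write w = 0.40 for walk response, c = 0.73 for the composite, and q = (0.50 − 0.17)/0.60 = 0.55 for class improvement among walk non-responders, assumed unrelated to distance. The factor is (1 − q)·w(1 − w)/[c(1 − c)] = 0.45 × 0.24/0.1971 = 0.55. That leaves about 0.14 to 0.18 per 100 m. Treating 100 m as one SD is a further assumption, since no baseline SD is given.

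**5. Gain for the primary endpoint.** Simulation of 60,000 trials per setting: 35 per arm, half in class III, 6MWD effect 0.16 per SD. The adjusted test is a permutation score test with stratum and 6MWD.

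| Stratum log odds ratio | Gain over Pearson, 73% v 40% | 65% v 40% |
|---|---|---|
| 0.12 to 0.29 | 0.5 to 0.7 points | 1.3 to 1.8 points |
| 0.57 | 1.0 point | 2.4 points |

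At 65% about 1 point appears even with no prognostic effect (53.5% to 54.5%). That part is test calibration, not covariate information.

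Stronger effects, for which the documents give no support, would bring more. At 1.0 for the stratum and 0.5 per SD, the gain is 3.4 to 4.4 points at 73% and 5.4 to 7.7 at 65%, and Pearson's size falls to 3.6–4.3%.

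**6. Continuous endpoints (correlation ρ with own baseline assumed).**

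| Comparator | Variance cut | ρ = 0.5 | ρ = 0.8 |
|---|---|---|---|
| Unadjusted week 12 | ρ² | 25% | 64% |
| Change score | 1 − (1 + ρ)/2 | 25% | 10% |
| Planned model, listed covariates explain 10% | 1 − (1 − ρ²)/0.9 | 17% | 60% |
| Planned model, they explain 20% | 1 − (1 − ρ²)/0.8 | 6% | 55% |

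The last two rows assume that the listed covariates add nothing beyond the own baseline. Against the unadjusted comparison at ρ = 0.5, 35 per group is worth 35/0.75 ≈ 47.

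**The case against.** The strongest reply is that the plan already contains most of the remedy. The logistic model lists baseline 6MWD and functional status, which presumably means WHO class, and the open wording leaves own baselines unnamed, not excluded. That Pearson or Fisher comes first rests on sentence order and on the sample size matching an unadjusted test; no ranking is stated. All this stands. It narrows the point to an unranked, unfixed analysis and a modest loss of efficiency.

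The stratum pools class I with class II, so adjusting for it only partly captures the patients who cannot improve a class. That also stands, and is one reason why the gain is small. The continuous endpoints are secondary and carry no power claim, so their gain is in precision only.

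Adjustment also has costs at this sample size. In null simulations at 35 per arm, size was 4.8–5.4% for the Wald test of the three-term logistic model, 5.4–5.9% for the likelihood-ratio test and 4.7–5.2% for the within-stratum permutation test. A delta-method interval for the standardised risk difference excluded zero in 6.0–6.5% of null trials. The change is worthwhile only with a test and interval that have been checked.

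A reader might infer that ignoring the strata inflates the type I error or biases the comparison. It does not: the unadjusted Pearson test errs on the conservative side. Nor is 35 per group wrong, since it reproduces for the Pearson test.

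**Conclusion.** The point holds as a recommended improvement, not as an error that invalidates the trial. The plan stratifies by WHO class, then compares the primary composite with a test that ignores the strata, and leaves the adjusted model unranked and its covariates open.

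For the primary endpoint the gain is roughly 0.5 to 1 point at the planned rates and 1 to 2.5 points at an assumed 65% v 40%. These figures rest on assumed class I shares, an assumed 6MWD SD and assumed independence of class improvement and distance. The open choices matter as well: Fisher in place of Pearson would cost about 7 points, and taking whichever of Pearson and the three-term Wald test is significant raises the null rejection rate to 5.3–6.0%.

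The clearer gain is own-baseline adjustment for continuous endpoints other than 6MWD. Its size depends on correlations that the documents do not give, and it is smaller against the planned covariate-adjusted models than against the unadjusted tests. Goal attainment and patient satisfaction have no baseline and are outside this point.

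**What to change.** In 1.24 and the matching summary text:

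- Name one primary analysis of the composite, adjusted for the randomisation stratum (I/II v III) and continuous baseline 6MWD. Fix these covariates before outcome data are analysed. This matters more here because section 1.25 notes that some of the team know both assignments and endpoints.
- Use a test whose size has been checked at 35 per arm, for example a within-stratum permutation of the adjusted score. If a standardised risk difference is reported, check its interval too, for example with a bootstrap; do not adopt the delta-method interval unchecked.
- Keep unadjusted Pearson as supportive, and Fisher only for sparse binary endpoints such as death.
- Analyse each continuous endpoint that has a screening or run-in value by ANCOVA on that value plus the stratum, on a log or rank scale if skewed.
- Give the same covariate list in both places; study site is now in one only.

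The cost is wording and a size check, with no new data. The odds ratio becomes conditional, which is why a standardised risk difference is useful beside it. Three model terms are about the limit: one pairwise comparison has 35 × 0.60 + 35 × 0.27 ≈ 30 non-responders at the planned rates, about 10 per term.

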1.22.8 Blood Biomarkers

a. HOMA-IR

Insulin resistance will be quantified using the homeostatic model assessment of insulin resistance (HOMA-IR), which estimates insulin resistance through fasting plasma insulin and glucose ratios, at screening and 12 weeks.

b. Lipid Metabolism

Altered lipid metabolism reflects insulin resistance. Fasting plasma lipid metabolites will be evaluated via non-targeted metabolomics screen. Mass spectroscopy of approximately 300 metabolites across all major metabolic pathways will be performed at screening and 12 weeks.

c. Fatty Acid Metabolism

Elevated circulating fatty acids and acylcarnitines contribute to RV lipotoxicity and indicate insulin resistance associated with pulmonary hypertension. To evaluate the effect of this intervention on fatty acid metabolism, we will measure fasting long-chain fatty acid and acylcarnitine profiles using mass spectrometry at screening and 12 weeks.

d. Plasma and Urine Estradiol and Estrogen Metabolites

Estrogen metabolites are associated with pulmonary hypertension in human PAH subjects. Estrogen metabolism we will be evaluated by measuring plasma estradiol (E2) and estrogen metabolites, including 2ME and 16 α OHE, using mass spectrometry at screening and 12 weeks.

e. Plasma NT-proBNP

Plasma NT-proBNP reflects right ventricular function in PAH and is a strong predictor of outcome in PAH. BNP will be assessed at screening and 12 weeks.

f. Amino Acids and Metabolomics

We and others have observed in cross-sectional studies that PAH is associated with insulin resistance and lipid abnormalities. Metabolites associated with insulin resistance and lipid metabolism have not been examined in the context of a clinical trial targeting insulin resistance. Changes in amino acids and metabolomic profiles with metformin and physical activity may provide insight into the mechanisms by which these interventions may improve insulin resistance (and outcomes) in patients with PAH.

g. Safety Labs

A comprehensive panel, complete blood count, hemoglobin A1c, and a urine pregnancy test will be assessed at screening and 12 weeks.

1.22.9 *Transthoracic Echocardiographic Measures*

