1.26 Statistical Power

The pivotal trial of Iloprost demonstrated that in the Iloprost arm nearly 40% had 10% improvement in 6MWD, 50% had improved FC, and 17% had both¹. From these data we calculate that 73% had either 10% improvement in 6MWD or improved functional status. Assuming metformin or the exercise arm will have similar response rate, and the placebo group will have 40% response rate, thought to be due to training effect potentially, we need 35 per group to have 80% power at 0.05 type I error rate. For the metformin and exercise combination group, an additive or synergistic effect between the two interventions will put its response rate above 73%. Thus, the combination vs. placebo comparison will have at least 80%, likely better power. From past experience coupled with the low risk, low side effect profile interventions, we estimate a dropout rate of less than 10%¹. We will enroll 40 subjects to ensure 35 completed subjects per group. The total target enrollment is 160 over 4.5 years.

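### For right-skewed secondary biomarkers the plan fixes neither the outcome scale nor adjustment for the endpoint's own screening value, so no named method is set up to combine skew-robustness with baseline adjustment

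*Combined protocol and SAP*

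**What the plan says.** Section 1.24 has one recipe for every continuous endpoint. The unadjusted step is: "Continuous endpoints will be analyzed using either two-sample t-test or ANOVA, or non-parametric methods Wilcoxon Rank Sum test or Kruskal-Wallis test". No rule says when the parametric or the rank method applies. The adjusted step is: "Multivariable regressions (general linear models) will be conducted to examine the treatment effect while adjusting for important covariates". The covariates are described as "important covariates such as baseline 6MWD, functional status, age, and study site". The Data Analysis part of the Protocol Summary repeats this without study site.

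The documents nowhere mention a log or other transformation, a geometric mean, or an adjusted rank or ordinal model. They do not name a biomarker's own screening value as a covariate. That value is collected: section 1.22.8 and Table 2 place the blood biomarkers at screening and at week 12, and section 1.15 defines a run-in baseline for daily steps.

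HOMA-IR is described in section 1.22.8 as a measure that "estimates insulin resistance through fasting plasma insulin and glucose". Section 1.22.10 expresses triglyceride content (%TG) as a ratio of two signal amplitudes, and only participants in the Vanderbilt sub-study have it.

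**The concern.** HOMA-IR, NT-proBNP, estradiol and its metabolites, free fatty acids, acylcarnitines and %TG are positive quantities. Right skew and proportional treatment effects are reasonable working assumptions for them. In a linear model on the measured scale, a few large values then dominate both the estimate and its standard error. A rank test on week-12 values withstands the skew but ignores the screening value. A linear model on the log scale, with the log screening value as covariate, deals with both and needs only data already collected.

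Two things are at stake. The first is power and precision for the endpoints that carry the mechanistic aim; section 1.27 expects the trial to inform later studies even if it is null. The second is prespecification. With the scale and the choice between parametric and rank methods left open, the analyst can settle both after seeing the data. Section 1.25 itself notes that the trial is single-blinded and that some team members know both allocation and endpoints.

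**Working it through.** **1. Inputs from the documents.** The number of completers comes from section 1.26: "We will enroll 40 subjects to ensure 35 completed subjects per group". It rests on the binary primary endpoint, with the active rate taken from a trial in which "73% had either 10% improvement in 6MWD or improved functional status", and with the assumption that "the placebo group will have 40% response rate".

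**2. The plan's own figure.** With p1 = 0.73, p2 = 0.40, mean 0.565, and two-sided alpha 0.05 (the sidedness is not stated, but two-sided reproduces the result):

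n = [1.96·√(2·0.565·0.435) + 0.8416·√(0.73·0.27 + 0.40·0.60)]² / 0.33² = (1.374 + 0.556)² / 0.1089 ≈ 34.2, so 35 per group, with power 80.9%.

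This agrees with "we need 35 per group to have 80% power at 0.05 type I error rate". With 10% dropout, 35/0.90 = 38.9, so 40 enrolled is enough. It is the only power figure in the documents; none is given for a continuous endpoint.

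**3. Assumed inputs.** The documents give no SD, distribution or correlation for any continuous endpoint. Assumed: log-normal outcome, log SD 0.5 to 1.2, screening-to-week-12 correlation ρ of 0.5 or 0.7, true 30% reduction (log ratio ln 0.70 = −0.357), 35 v 35, two-sided 0.05. The own screening value is in both regression models, so that they differ only in scale.

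**4. Power at ρ = 0.7** (3,000 simulated trials per row):

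| Log SD | Linear model, measured scale | Linear model, log scale | Gain (points) | Wilcoxon, week-12 values |
|---|---|---|---|---|
| 0.5 | 95.8% | 98.0% | 2.2 | 82.4% |
| 0.8 | 53.3% | 72.7% | 19.4 | 43.0% |
| 1.0 | 34.2% | 53.8% | 19.6 | 29.9% |
| 1.2 | 20.2% | 39.8% | 19.6 | 21.2% |

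Hand check of the log-scale column at log SD 0.8: SE = 0.8·√((1 − 0.49)·2/35) = 0.1366; 0.357/0.1366 = 2.61; power ≈ Φ(2.61 − 1.96) = Φ(0.65) ≈ 74%. Repeat simulations moved individual gains by up to about 3 points.

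**5. Gain at ρ = 0.5**, log scale over measured scale: about 5, 13, 14 and 13 points at log SD 0.5, 0.8, 1.0 and 1.2.

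**6. Wider range.** Here the effect was set so that the log-scale model has about 80% power, with log SD 0.3 to 1.3 and ρ from 0 to 0.8 (5,000 trials per setting).

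- Measured-scale model: it loses 1.5 to 3 points at log SD 0.3, 6 to 8 at 0.5, 10 to 15 at 0.7, 19 to 27 at 1.0, and 29 to 39 at 1.3.
- Week-12 Wilcoxon: the loss hardly depends on skew. It is about 2 points at ρ = 0, 5 at 0.3, 13 to 14 at 0.5, 29 to 31 at 0.7, and 41 to 42 at 0.8. This loss comes from omitting the baseline.

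**The case against.** The strongest reply is that the plan's silence is not a rule. A general linear model can be fitted to a logged outcome, and the covariate list is open-ended, so the remedy is compatible with the present text. That stands. A reader might infer that the plan prescribes the measured scale, or that the analyst can never have adjustment and robustness together. The documents support neither. What they show is that the scale and the own-baseline covariate are not specified.

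A second reply is that a rank test can use the screening value if it is run on the week-12/screening ratio. This is largely right at ρ = 0.7. Power is then about 96%, 65%, 46% and 33% at log SD 0.5, 0.8, 1.0 and 1.2, against 99%, 74%, 53% and 39% for the log-scale model in the same run, a gap of 3 to 9 points. It does not help at ρ = 0.5: the log ratio has variance 2(1 − ρ)σ² = σ², the same as the week-12 value alone, whereas baseline adjustment leaves (1 − ρ²)σ² = 0.75σ². Nor does the plan specify the ratio form.

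A third reply is that exactly log-normal data with a purely multiplicative effect favour the log model by construction. That also stands, and it is why the size is given as a range tied to its assumptions.

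Three further inferences go too far:

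- Step count need not be strongly skewed. At log SD 0.3 to 0.5 the measured-scale model loses only about 1.5 to 8 points.
- The 35 v 35 figures do not carry over to %TG, which comes from a smaller sub-study at one site.
- HOMA-IR is not the direct test of the trial's hypothesis. The Abstract states that hypothesis in terms of exercise capacity and WHO functional class, and HOMA-IR is one of 41 unranked secondary aims.

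**Conclusion.** The concern holds as a gap in specification. No method named for continuous endpoints is set up to combine adjustment for the endpoint's own baseline with robustness to right skew, and the outcome scale and the choice between parametric and rank methods are left open.

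For log-normal data, 35 v 35, a 30% reduction and ρ of 0.5 to 0.7, the log-scale model gains about 2 to 5 points over the measured-scale model at log SD 0.5 and about 13 to 21 points at log SD 0.8 to 1.2. Across wider assumptions the loss from the named methods runs from about 2 to about 40 points. A reader might take 20 points as a fixed loss or an upper limit. It is neither, because the documents supply no SD or correlation from which to derive one.

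The binary primary endpoint and its sample size are unaffected. The change is worth making, but it does not threaten the main conclusion of the trial.

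**What to change.** In section 1.24 and the Data Analysis part of the Protocol Summary:

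- State that HOMA-IR, NT-proBNP, estradiol and estrogen metabolites, free fatty acids, acylcarnitines and, in the sub-study, %TG are analysed by the general linear model on the log scale, with the log screening value as covariate. Report geometric mean ratios with 95% CI.
- Keep the rank test for these endpoints as a named sensitivity analysis, and say whether it is applied to week-12 values or to the week-12/screening ratio.
- Adjust average daily step count for its run-in value, with the log scale optional.
- For the remaining continuous endpoints, state the scale and the rule for choosing a parametric or a rank method.

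The cost is SAP wording; no new data, visits or subjects are needed. The small downside is that effects on the logged endpoints are reported as ratios rather than absolute differences.
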